Primary aim. We will test the noninferiority of the erector spinae nerve block compared to the paravertebral nerve block. The 95% confidence interval (CI) associated with the Wilcoxon-Mann-Whitney test will be derived for the group difference (paravertebral minus erector spinae) in median pain scores within the recovery room. If the lower limit of the 95% CI is greater than -1.25, we will conclude noninferiority. If there are significant differences between the groups in any key characteristics, these characteristics will be included as covariates in a linear model. The same noninferiority margin (-1.25) will be applied to the 95% CI for the covariate adjusted group difference in mean pain derived from the linear model.

The noninferiority of the erector spinae nerve block with regard to total opioid consumption within the operating and recovery rooms will be tested in the same manner as pain, i.e. comparing the limits of a 95% CI associated with the Wilcoxon-Mann-Whitney test to a predefined noninferiority margin (in this case 2 mg). Covariate adjusted linear models will again be applied in the event that key characteristics are significantly different between the groups.

Sample size justification. Power for the Wilcoxon-Mann-Whitney derived noninferiority testing is based on 10,000 simulated trials. We simulated pain scores from a discrete distribution with median (interquartile range) 3 (2-5) [Kairaluoma, 2004]. Between the quartiles, the probability of each score was assumed constant. The distribution for each group was assumed to be the same. The sample size of n=50 per group provides 82% power to detect noninferiority in pain with a margin of 1.25. Similarly, opioid consumption was assumed to follow a truncated normal distribution with mean 2.5 mg and standard deviation 2 mg, and minimum value 0 mg. The sample size of n = 50 per group provides at least 95% power to detect noninferiority with margin 2 mg. Therefore, we will enroll 50 subjects for each of two treatments with a total enrollment of 100 subjects. To allow for dropouts, we will request a maximum enrollment of 120 subjects. Noninferiority in pain is tested first, and if significant, noninferiority in opioid consumption is tested. Under this hierarchical testing framework, no adjustment in alpha is necessary to control Type 1 error [Mascha, et al 2012].

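### The pain interval is labelled as a difference in group medians, but the Wilcoxon-Mann-Whitney interval estimates the Hodges-Lehmann shift, so a non-inferiority claim about medians would not follow from it

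*Combined protocol and SAP*

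**What the plan says.** Section 9, Primary aim, sets the pain analysis: the 95% interval that goes with the Wilcoxon-Mann-Whitney test "will be derived for the group difference (paravertebral minus erector spinae) in median pain scores within the recovery room". The decision rule follows: "If the lower limit of the 95% CI is greater than -1.25, we will conclude noninferiority". Neither the Hodges-Lehmann estimate, nor a shift model, nor pairwise differences are mentioned anywhere.

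If baseline characteristics differ significantly, a linear model takes over: "The same noninferiority margin (-1.25) will be applied to the 95% CI for the covariate adjusted group difference in mean pain". That is a further quantity, a mean difference. It is noted here only because the contrast with a group mean shows that the preceding sentence means group medians.

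The sample size paragraph plans on a pain distribution with median 3 and interquartile range 2 to 5, adds that "Between the quartiles, the probability of each score was assumed constant", and that "The distribution for each group was assumed to be the same". It reports 82% power at 50 per group. Opioid consumption is tested by the same method against 2 mg, with no separate statement of what is estimated.

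**The concern.** The interval and its label refer to different population quantities. The Wilcoxon-Mann-Whitney interval locates the median of the differences between a paravertebral and an erector spinae subject, taken over all pairs. The difference between the two group medians is something else. The two coincide under a location shift, but need not when one arm's distribution differs in shape from the other's.

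This matters because the pain result is the first gate of the primary claim: opioid use is tested only if pain passes. A report that follows the label could state non-inferiority in median pain when the true medians differ by more than 1.25 points, and could print an interval that does not describe the two medians beside it.

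**Working it through.** **Inputs from the plan.** Margin -1.25 on the lower limit of a two-sided 95% interval (one-sided 0.025); 50 per group; planning quartiles 2, 3, 5; identical arms; power 82%.

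**Assumptions.** Integer scores from 0 to 10 (the plan gives no range for the pain scale). Planning distribution with 25% of subjects in each of 0-2, 3, 4-5 and 6-10, spread evenly within each band: 1/12 on each of 0, 1, 2; 0.25 on 3; 0.125 on each of 4, 5; 0.05 on each of 6 to 10. Its quartiles are 2, 3, 5, its share of zeros is 1/12 = 8%, and its mean is 0.25 + 0.75 + 0.50 + 0.625 + 2.00 = 4.125.

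**1. What the interval estimates.** With X for paravertebral and Y for erector spinae, form the 50 × 50 = 2,500 differences X - Y. Their median is the Hodges-Lehmann estimate. The lower 95% limit is approximately the ordered difference at rank n²/2 - 1.96 × √(n²(2n+1)/12) = 1,250 - 1.96 × √(2,500 × 101/12) = 1,250 - 1.96 × 145.06 ≈ 966. The group medians do not enter.

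**2. The plan's own figure.** With both arms on the planning distribution, this rule gives 80.4-81.8% power over 10,000 trials, depending on tie and continuity corrections, and 80.8% over 100,000. Other layouts on 0-10 with quartiles 2, 3, 5 give 78-87%. The stated 82% is therefore reproduced for the shift interval. A percentile bootstrap interval for the difference in medians (1,000 resamples, 3,000 trials) gives about 54% under the same distribution.

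**3. Different shapes, many zeros (assumed).** Each arm is the planning distribution with a fraction z of extra zeros, so P(0) = z + (1 - z)/12.
- Paravertebral, z = 0.45: P(0) = 0.496 and P(≤1) = 0.542, median 1. With z = 0.50: P(0) = 0.542, median 0.
- Erector spinae, z = 0.30: P(≤2) = 0.475 and P(≤3) = 0.65, median 3. With z = 0.20: P(≤2) = 0.40 and P(≤3) = 0.60, median 3.

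| Extra zeros, paravertebral vs erector spinae | True medians | Non-inferiority declared |
|---|---|---|
| 45% vs 30% | 1 vs 3 | about 46-49% |
| 50% vs 30% | 0 vs 3 | about 34-37% |
| 45% vs 20% | 1 vs 3 | about 15-17% |
| 50% vs 20% | 0 vs 3 | about 9% |

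The ranges are across independent simulation runs. In the first row the true shift is 0 and the mean difference is (0.55 - 0.70) × 4.125 = -0.62.

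**4. Different shapes, 8% zeros in each arm (assumed).** Paravertebral follows the planning distribution, median 3. Erector spinae has 1/12 on each of 0, 1, 2; 0.20 on 3; 0.04 on 4; 0.25 on 5; 0.06 on 6; 0.05 on each of 7 to 10. The cumulative probability is 0.49 at 4 and 0.74 at 5, so the median is 5. The true shift is 0 and the mean difference is 4.12 - 4.32 = -0.20. Non-inferiority is declared in about 55-57% of trials, against about 8% with the bootstrap interval for the medians. A second shape with the same medians and share of zeros, but a true shift of -1, gives about 39%.

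**5. Near-pure shift.** Moving the planning distribution up 2 points, capped at 10, gives medians 3 vs 5 and a true shift of -2. Non-inferiority is declared in about 0.1% of trials.

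**The case against.** The strongest reply is that the test, margin and power already agree with each other. All belong to the shift, Hypothesis 1 speaks of analgesia on the Numeric Rating Scale without naming medians, and correcting the label changes no decision. That stands, and it is why this is a matter of wording. It does not rescue the sentence that says what the interval is for.

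The examples are also built to produce disagreement: they put one median just across a gap in the distribution, and the mean differences are modest. That stands too. Mixtures closer to the planning distribution (10% vs 0%, 15% vs 0% and 20% vs 5% extra zeros) leave both medians at 3. Sample medians can also be unstable: with identical arms carrying 45% extra zeros, 11% of trials declare non-inferiority while the observed medians differ beyond the margin. Two discordant observed medians are therefore not, alone, evidence that the rule failed.

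The wording might instead mean each subject's own median recovery-room score. This would remove the mislabel, but it fits poorly with the contrast to a group difference in mean pain. If it is meant, the plan should say so.

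Four stronger readings are tempting and not supported:
- That the scores will contain many zeros. The planning lower quartile is 2, so fewer than 25% zeros, and section 10 enrols patients expected to have at least moderate pain. The point does not need this premise, as step 4 shows.
- That shift and median difference agree only under an exact shift. That is sufficient, not necessary: symmetric distributions with different spreads also agree.
- That the rule fails to hold its 2.5% error rate in general. The examples show this only for a claim about medians, when the arms differ in shape.
- That 54% means the trial is too small. That figure belongs to an analysis the plan does not use.

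**Conclusion.** The point holds as a mislabelled estimand for the primary pain endpoint. The interval is for the Hodges-Lehmann shift, and the plan calls it the difference in group medians. With true medians 2 to 3 points worse under erector spinae, the rule declares non-inferiority in about 9-49% of trials in the many-zeros examples and about 39-57% with 8% zeros per arm, but in under 1% under a near-pure 2-point shift. These figures assume integer 0-10 scores, 50 per arm and constructed distributions; they show that a false claim about medians is possible, not how likely it is. The 82% power is sound for the shift and does not describe a comparison of medians. Nothing here shows the planned test, margin or sample size to be wrong.

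**What to change.** In section 9, Primary aim, name the Hodges-Lehmann shift (the median of all paravertebral-minus-erector-spinae pairwise differences) as the quantity estimated and compared with -1.25, and word the non-inferiority conclusion in the same terms. Report group medians descriptively and make no non-inferiority claim about medians from this interval. Use the same wording for opioid consumption and its 2 mg margin. A bootstrap interval for the difference in medians may be added as support but is not required.

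The cost is a few words in the statistical section. The test, margin, enrolment and 82% power are unchanged. The one drawback is a headline quantity that is slightly less intuitive than a difference in medians.

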9. RESEARCH DESIGN AND METHODS

This investigation will be a randomized, subject-masked, active-controlled parallel-arm, human subjects clinical trial. Of note, we will be using standard-of-care local anesthetic under an FDA-approved purpose and do not plan to research a possible change of indication or use of these medications as part of this research project. The treatments in both groups are currently used at our institution and there is true clinical equipoise at this time. The only difference in treatment between subjects who enroll versus those not enrolled in this study will be those who enroll will have the decision between which anatomic block location determined randomly, as opposed to the physician simply choosing him/herself.

Enrollment. Consenting adults undergoing breast surgery with a planned single-injection regional analgesic will be offered enrollment. Patients undergoing breast surgery with a planned perineural catheter regional analgesic will be excluded. Study inclusion will be proposed to eligible patients prior to surgery. If a patient desires study participation, written, informed consent will be obtained using a current UCSD IRB-approved ICF. Selection for inclusion will not be based on gender, race, or socioeconomic status. The study population of interest includes men and women of all races and socioeconomic status. Inclusion and exclusion criteria are listed in section #9 below.

Preoperative Procedures. Following written, informed consent, we will collect baseline anthropomorphic information (e.g., age, sex, height, and weight). All subjects will have a peripheral intravenous (IV) catheter inserted, standard noninvasive monitors applied, supplemental oxygen administered via a nasal cannula or face mask, and placed in the sitting position. Midazolam and fentanyl (IV) will be titrated for patient comfort, while ensuring that patients remain responsive to verbal cues. Both possible block locations will be viewed with ultrasound. If one or both of the locations is unacceptable for block placement in the clinician's opinion, the subject will not be randomized and will not proceed further with the study.

Subjects will then be randomized using a computer-generated list and opaque, sealed envelopes to

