Outcome measurements (end points). Pain scores will be recorded using the NRS. Within the recovery room, pain scores, opioid requirements, and antiemetic administration will be recorded by nursing staff masked to treatment group. The morning following surgery, all subjects will be contacted by phone or in person [if hospitalized] to record lowest, average, highest, and current pain scores; sleep disturbances, and nausea using a 0-10 Likert scale (0 = no nausea; 10 = vomiting). For outpatients, opioid requirements will be recorded while inpatients will have opioid requirements extracted from the electronic medical record. In addition, we will extract antiemetic use from the electronic record. We will collect the times at which subjects felt their block resolve and they consumed their first opioid analgesic pills following recovery room discharge.

Hypothesis 1: Following breast surgery, **analgesia** will be non-inferior in the recovery room with an erector spinae plane block compared with a paravertebral block as measured with the Numeric Rating Scale.

Hypothesis 2: For breast surgery, **opioid** consumption will be non-inferior in the operating and recovery rooms with an erector spinae plane block compared with a paravertebral block (primary: cumulative intravenous morphine equivalents).

Primary end point: In order to claim that erector spinae plane blocks are non-inferior to paravertebral

blocks, both Hypotheses 1 and 2 must be at least non-inferior.

Statistical methods. Descriptive statistics will be provided by arm and in aggregate. Baseline characteristics of arms will be compared using the Wilcoxon-Mann-Whitney and Fisher's Exact tests. Key characteristics that are significantly different (p<0.05) will be included as covariates in the analysis models.

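### Baseline significance tests choose the analysis that decides pain noninferiority, and the stated 82% power covers only the Wilcoxon branch

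*Combined protocol and SAP*

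**What the plan says.** All of this is in Section 9 of the combined protocol and SAP.

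- **Statistical methods.** Baseline characteristics are compared between arms by Wilcoxon-Mann-Whitney and Fisher's exact tests, and "Key characteristics that are significantly different (p<0.05) will be included as covariates in the analysis models". The key characteristics are neither listed nor counted. The Preoperative Procedures paragraph gives age, sex, height and weight as examples of baseline data.
- **Primary aim.** By default, the lower Wilcoxon limit for paravertebral minus erector spinae must lie above -1.25. Then: "If there are significant differences between the groups in any key characteristics, these characteristics will be included as covariates in a linear model". For that model, "The same noninferiority margin (-1.25) will be applied to the 95% CI for the covariate adjusted group difference in mean pain". Opioid consumption follows the same pattern with a 2 mg margin.
- **Sample size justification.** "Power for the Wilcoxon-Mann-Whitney derived noninferiority testing is based on 10,000 simulated trials", with both groups drawn from one discrete distribution (median 3, quartiles 2 and 5). The result: "The sample size of n=50 per group provides 82% power to detect noninferiority in pain with a margin of 1.25". No power is given for the linear model or for the two analyses used as one rule.
- **Testing order.** "Noninferiority in pain is tested first, and if significant, noninferiority in opioid consumption is tested". Section 6 requires both endpoints to be noninferior before the overall claim is made.

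**The concern.** In a randomized trial a baseline p<0.05 is largely a chance event. Here that event changes two things at once: the effect measure (a Wilcoxon shift or a difference in means) and how hard the test is to pass. Covariates enter because they happen to be unbalanced, not because they are expected to predict pain. The factor the design itself stratifies on, unilateral versus bilateral surgery, is held balanced by blocks of 4, so the switch will hardly ever select it.

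Pain is the gate. If a chance imbalance in height, say, moves the decision to an analysis that fails, opioid consumption is not tested and the noninferiority claim is lost, even where the Wilcoxon interval would have passed. The chance of this depends on how many characteristics are tested, which the plan leaves open.

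**Working it through.** **Inputs from the plan.** n=50 per arm; equal groups; margin 1.25; two-sided 95% CI; median 3, quartiles 2 and 5, even probability between quartiles; baseline tests at 0.05.

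**Assumed, because the plan does not give them.** One integer score per subject; 25% probability on each of {0-2}, {3}, {4-5} and {6-top}, with top score 10 (SD 2.70) or 9 (SD 2.48); the number and type of key characteristics; the share of latent pain variance they explain (0-35%).

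**1. Reproduce the 82%.** The lower Wilcoxon limit is an ordered value among the 50 x 50 = 2,500 pairwise differences, at rank 1250 - 1.96 x sqrt(2500 x 101/12) = 1250 - 284.3, i.e. the 965th smallest. Simulated power is 80-83%, so the stated figure is reproduced.

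**2. Linear branch at the same margin.** Without covariate gain, power = Phi(1.25/(SD x sqrt(2/50)) - 1.960).
- SD 2.70: 1.25/0.540 = 2.315; Phi(0.355) = 64%.
- SD 2.48: 1.25/0.496 = 2.520; Phi(0.560) = 71%.

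In trials that actually switch, the simulated linear model passes in 58-73%, against 76-83% for Wilcoxon in the same trials. Adjusting for an unbalanced covariate that predicts little widens the interval.

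**3. Why the branches differ.** Differences between integer scores are integers, so the Wilcoxon limit is an integer. A limit of -1 passes and -2 fails, whether the margin is 1.25 or 1.99. The linear model applies 1.25 literally.

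**4. Chance of switching.** For k independent tests, 1 - 0.95^k: 18.5% for k=4 and 33.7% for k=8. Fisher tests on sparse binary items trigger less often.

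**5. The rule as written** (20,000 trials per setting; ranges run over 0-35% explained variance):

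| Characteristics (assumed mix) | Top score | Switch | Wilcoxon alone | Rule as written |
|---|---|---|---|---|
| 4 (3 continuous, 1 binary at 2%) | 10 | 14% | 81% | 78-79% |
| 4 (same) | 9 | 14% | 83% | 81-82% |
| 8 (4 continuous, 4 binary) | 10 | 25-26% | 80-81% | 75-77% |
| 8 (same) | 9 | 25-26% | 83% | 79-80% |

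Hand check, top score 10, using 81% for Wilcoxon and 60% for the linear model: 0.86 x 0.81 + 0.14 x 0.60 = 78%; 0.75 x 0.81 + 0.25 x 0.60 = 76%.

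The assumed mix matters. Four independent characteristics with a commoner binary item (30%) gave a 17% switch rate and 77% against 81%, the lower end for four. Eight independent continuous characteristics gave 74-76%. Conversely, if a single tested characteristic explains 20% or more of the variance, nothing is lost (81-84% either way).

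**6. Continuous scores with the same quartiles,** Wilcoxon against the mean-difference interval: 74-75% vs 67% (top 10), 77-78% vs 76% (top 9), 80-81% vs 83% (top 8), 86% vs 90% (top 7).

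**7. False noninferiority.** With a true mean worsening of 1.25 and integer scores, Wilcoxon passed about 6-11% of trials, depending on the assumed form of the worsening. The mean-difference CI passed about 2-3%.

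**8. Stratum.** In 4,000 stratified block-of-4 randomizations of 100 subjects (20%, 40% or 50% bilateral), the smallest Fisher p was 0.74.

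**9. Opioids.** Under the plan's distribution both analyses exceed 99% power at 2 mg, so the switch costs nothing there.

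**The case against.** **The switch is inferred.** The Primary aim paragraph says without condition that a Wilcoxon limit above -1.25 establishes noninferiority, and it never says that the linear model overrides this. If the model was meant as supplementary, no power is lost. That stands as a caution. But the model is given its own margin test and nothing marks it as secondary, so on that reading the plan has two tests and no statement of which decides. The same edit cures both.

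**The linear branch is not inherently weaker.** This stands. Recovery-room pain is recorded as several scores, and the plan does not define one value per subject. If the value is an average, the gap shrinks or reverses (step 6). With integers, part of the Wilcoxon advantage is leniency on the mean scale (step 7), so keeping Wilcoxon is not free.

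**The loss is small.** With the four named examples it is about 1-4 points, similar to the uncertainty in rebuilding the 82%: other placements of the boundary scores gave 73-88%. This also stands, and it limits the weight of the power argument.

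**Imbalance need not be pure chance.** Section 9 allows subjects with misplaced blocks to be excluded after randomization, so the analysed groups, and the stratum, could drift. Hence largely chance, and hardly ever rather than never.

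**Conclusion.** The concern holds as a prespecification fault of modest numerical size. On the natural reading, baseline tests pick the analysis that decides the gatekeeping endpoint, and no power is stated for that rule. With one integer score per subject it is about 77-82% for the four example characteristics and about 75-80% for an assumed eight of mixed type. These figures rest on the assumed top score, covariate mix and explained variance, and they do not carry over to averaged scores.

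Three stronger conclusions that a reader might draw are not supported:

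- *The 82% is wrong.* It is reproducible, and the plan claims it only for the Wilcoxon test.
- *Power falls to 73% or below.* With mixed characteristics that takes about twelve. No document gives such a number, and the word key suggests a short list.
- *The switch makes false noninferiority more likely.* In a check at a true mean worsening of 1.25, the rule as written passed 6% of trials and Wilcoxon alone 7-8%. The switch moves some trials to the stricter test.

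**What to change.** Before any comparison by arm:

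1. Delete the baseline p<0.05 condition from Statistical methods and Primary aim, and name one analysis that decides pain noninferiority. Keeping the Wilcoxon 95% CI against -1.25 matches the stated 82% and n=50.
2. Always report a covariate-adjusted linear model as a supporting analysis, with covariates named in advance and including the unilateral/bilateral stratum.
3. Use the same structure for opioid consumption.
4. Define the per-subject recovery-room pain value. State that the 82% refers to the Wilcoxon rule, and rerun the simulation if the value is not a single integer score.
5. Report how the chosen rule behaves at a true worsening of 1.25.

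**Cost.** Wording and a short simulation; no added subjects or data. Two things are given up. The adjusted result no longer decides: where a single strong predictor (20-35% of variance) happens to be unbalanced, the linear model would have had 71-85% power against 66-72% for Wilcoxon. And with integer scores the sponsor accepts the more lenient test on the mean scale, which should be a stated choice.

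Making the linear model the sole rule is possible but harder. For 82% power, n per arm = 2 x ((1.960 + 0.915) x SD/1.25)^2, which is 66 (SD 2.48) to 77 (SD 2.70), or 53-62 if covariates explain 20% of the variance. The ceiling is 120/2 = 60 per arm, and that allowance is meant for dropouts: "To allow for dropouts, we will request a maximum enrollment of 120 subjects".

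### Is the 82% power for pain misleading because, on whole-number scores, a margin of 1.25 acts like any margin between 1 and 2?

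*Combined protocol and SAP*

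**What the plan says.** Section 9 (Primary aim) bases the pain test on the 95% interval attached to the Wilcoxon-Mann-Whitney test, for paravertebral minus erector spinae: "If the lower limit of the 95% CI is greater than -1.25, we will conclude noninferiority".

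Baseline imbalance leads to an adjusted analysis. Under Statistical methods, "Key characteristics that are significantly different (p<0.05) will be included as covariates in the analysis models"; under Primary aim, the adjusted analysis is a linear model and "The same noninferiority margin (-1.25) will be applied to the 95% CI for the covariate adjusted group difference in mean pain".

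On power, the Sample size justification says "Power for the Wilcoxon-Mann-Whitney derived noninferiority testing is based on 10,000 simulated trials". The arms are identical, and pain is discrete with median 3 and quartiles 2 and 5. On shape, it adds: "Between the quartiles, the probability of each score was assumed constant". The result is "The sample size of n=50 per group provides 82% power to detect noninferiority in pain with a margin of 1.25". The section does not give the lowest and highest simulated scores, the standard deviation, or the power of the linear model.

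Under Outcome measurements, "Within the recovery room, pain scores, opioid requirements, and antiemetic administration will be recorded by nursing staff masked to treatment group". The text does not say how several readings become one score per patient.

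**The concern.** The limits of a Wilcoxon-Mann-Whitney interval are ordered pairwise differences between patients. If every score is a whole number, every limit is a whole number, and no limit can fall strictly between -2 and -1. The 1.25 then does no work that 1.01 or 1.99 would not do. In the linear model the limits are continuous and 1.25 operates as written, so one margin governs two tests that behave differently.

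Pain is tested first, and both pain and opioid use must succeed for the primary claim. If the margin were nominal only, a report of having excluded 1.25 points might be weaker than it sounds. If a chance imbalance moved the trial to the linear model, the 82% would no longer describe its power.

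**Working it through.** **1. Reproduce the 82%.** The plan supplies 50 per arm, identical arms, median 3, quartiles 2 and 5, and a two-sided 95% interval. The tails are an assumption. The base layout puts 25% evenly on each of 0-2, 3, 4-5 and 6-10 (mean 4.125, SD 2.70). The lower limit is the k-th smallest of 50 × 50 = 2,500 pairwise differences:

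k = 2,500/2 − 1.96 × √(50 × 50 × 101/12) = 1,250 − 284.3 = 965.7, so the 965th.

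In 40,000 simulated trials the lower limits were:

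| Limit | -4 | -3 | -2 | -1 | 0 | 1 |
|---|---|---|---|---|---|---|
| Trials | 1 | 165 | 7,455 | 24,766 | 7,578 | 35 |

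Power at 1.25 is (24,766 + 7,578 + 35)/40,000 = 81.0%. A tie-corrected test and R's `wilcox.test` also give 80-81%. Six other layouts with the same quartiles give 86-93%, so 82% lies within what the unstated tails allow.

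**2. Is power flat?** Yes. From the same table, power is 81.0% at margins 1.001, 1.25, 1.5, 1.75 and 1.999. It is 7,613/40,000 = 19.0% if the limit must exceed -1, and 39,834/40,000 = 99.6% once -2 passes.

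**3. Is the error rate broken?** Let erector spinae patients be worse by 1 point with probability 1 − f and by 2 points with probability f. The mean worsening is 1 + f. At f = 0.25 it is 1.25, and the rule passes 7.6% of trials (7.6-9.1% over seven layouts), against 2.3-2.5% for the mean-difference interval.

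The Wilcoxon-Mann-Whitney interval, however, estimates the median pairwise difference, not the mean. With p0 the probability that two patients' scores tie when there is no shift,

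P(difference ≤ -2) = (1 − f)(1 − p0)/2 + f(1 + p0)/2 = 0.5 + p0(f − 0.5).

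In the base layout p0 = 3(1/12)² + 0.25² + 2(0.125)² + 5(0.05)² = 0.127. At f = 0.25, P(≤ -2) = 0.5 − 0.127/4 = 0.468, while P(≤ -1) = 0.588. The true median difference is therefore exactly -1, inside the margin, and a pass is correct for that target. The target reaches -2 at f = 0.5, where the pass rate is 2.4-2.5%. A uniform 2-point shift passes about 0.1% of the time.

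**4. Would restating the criterion as at least -1 help?** With exact order-statistic limits it gives the same decision in every trial. R's limits lie within 0.0001 of a whole number, often just below it. In 2,000 R trials on the base layout, the rule as written passed 80.8% and a literal at-least-minus-1 rule passed 51.6%. The 29.2-point gap is numerical tolerance alone.

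**5. Fallback power.** With SE = SD × √(2/50) = 0.2 × SD, the normal approximation is Φ(1.25/SE − 1.96). At SD 2.70, SE = 0.54 and power is Φ(0.36) = 64%; simulation with t-intervals gives 63%. Simulated results by layout, unadjusted for the mean difference:

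| Quarters | SD | Wilcoxon-Mann-Whitney at 1.25 | Mean difference at 1.25 |
|---|---|---|---|
| 0-2, 3, 4-5, 6-10 | 2.70 | 81.1% | 63.1% |
| 0-2, 2-3, 3-5, 5-10 | 2.63 | 86.1% | 65.3% |
| 1-2, 3, 4-5, 6-10 | 2.54 | 88.1% | 68.6% |
| 0-2, 3, 4-5, 6-8 | 2.28 | 86.0% | 77.2% |
| 0-2, 2-3, 3-5, 5-8 | 2.20 | 90.1% | 80.3% |
| 1-2, 3, 4-5, 6-8 | 2.10 | 92.6% | 83.9% |
| 0-2, 3, 4-5, 6-7 | 2.09 | 91.2% | 84.7% |

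Covariates explaining 10% or 20% of the variance raise the first row to about 68% or 73%. By the normal formula, 82% needs a residual SD of 1.25/(2.875 × 0.2) = 2.17 or less.

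**The case for a change.** The strongest case for a change is that readers will take an excluded 1.25 as a statement about average pain. The Wilcoxon-Mann-Whitney rule does not control a mean worsening of 1.25 at 2.5%, whereas the linear model does. Which of the two applies depends on chance imbalance: with four independent characteristics each tested at 5%, it is triggered in 1 − 0.95⁴ = 19% of trials. Fallback power may then be well under 82%. Stating all this costs only some wording and a re-run of the simulation.

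Part of this stands. On whole-number scores the rule cannot separate margins above 1 and up to 2, and the two analyses are not equivalent tests. The fallback has lower power than the Wilcoxon-Mann-Whitney test in all seven layouts, and that power is not reported.

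What does not stand is that a stated figure is wrong or an error rate is lost. The 7.6% compares an interval for a median pairwise difference with a true value set on the mean. The plan attaches the 82% to the Wilcoxon-Mann-Whitney test by name and says the simulated scores are discrete. An interval ending at -1 does exclude -1.25. If the per-patient score is in effect continuous, for example an average of many readings, 1.25 operates as written: false non-inferiority is 2.2-2.5%, and power runs from 75% (scores 0-10) to 91% (scores 1-8).

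**Conclusion.** No change to the plan follows. The 82% reproduces at about 80-81% when scores are whole numbers running from 0 to 10. That it would also be the power at 1.5 does not make it false at 1.25. The test holds 2.5% error for its own target, and the fractional threshold is a sound way to write the rule because it is immune to small numerical error in the limits. Restating it would gain nothing with exact limits and could lose correct conclusions in software.

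What remains is detail that the plan leaves unwritten: the per-patient pain score, the simulated tails, and the power of the covariate-adjusted analysis. Analysts must settle the score to run the analysis at all. Writing down the other two would not alter the sample size, the criterion or any decision. The fallback figures (63-69% unadjusted for whole-number scores to 10, 77-85% if they stop at 7 or 8) describe a contingent analysis and rest on assumed tails. They are no basis for resizing the trial.

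The flat-power result assumes whole-number scores. The reproduced 82% assumes the base layout. The error-rate argument is algebraic for mixtures of 1- and 2-point shifts and holds for any whole-number layout.
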